When the anesthesiologist completes the preoperative evaluation for a patient who is flagged as having either respiratory disease or OSA and will receive general anesthesia, the anesthesiologist will receive a pop-up window reminding them of the best practice guidelines for pulmonary management in high-risk patients. As part of the study roll-out we will present these guidelines with our quality committee, but we anticipate that they will suggest 1) use of sugammadex to reverse neuromuscular blockade if rocuronium was used 2) use of objective train of four monitoring throughout the case and to confirm reversal 3) use of a tidal volume of 6-8 cc/kg 4) use of at least 5 cmH₂O of PEEP 5) positioning the head of the bed >30° after extubation.

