8.0 CLINICAL DECISION SUPPORT PATHWAY

The final clinical decision support pathway for clinician adherence involves preoperative and intraoperative phases. Clinicians will be trained prior to study go-live to ensure awareness and understanding of pathway procedures.

Preoperative Phase

1) Physicians/CRNAs will receive an alert identifying the patient as high-risk for postoperative pulmonary complications and the reason for the designation.
2) The notification will remind the provider to pick up study sugammadex from the OR pharmacy.
3) The notification will display the patient specific lung protective ventilation (LPV) parameters.

Intraoperative Phase

1) There will be a notification reminding the provider to get the study sugammadex.
2) If the patient has mechanical ventilation and the parameters are outside the LPV guidelines (5-7cc/kg and at least 5 of PEEP) an alert will pop up with the LPV recommendations.
3) If non-depolarizing NMB was given and it has been more than 30 minutes since TOF was documented (and last documentation was <100% and no subsequent NMB was given), then a popup will recommend checking twitches (note we will have the twitch monitor automatically populate into CC).
4) Reverse with Sugammadex.

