10.0 STUDY ENDPOINTSVariables/Time Points of Interest

- 1) **PACU Discharge Time (primary endpoint):** The duration in minutes from patient arrival in PACU until the ready for discharge order is placed by the anesthesiologist. This captures the time until they are clinically ready for discharge and eliminates noise such as the availability of beds that might effect actual discharge time
- 2) **Incidence of oxygen saturation <90%:** A binary variable indicating if the patient had any oxygen saturations below 90% from arrival in PACU until being marked for discharge
- 3) **Incidence of oxygen saturation <95%:** A binary variable indicating if the patient had any oxygen saturations below 95% from arrival in PACU until being marked for discharge
- 4) **Duration of supplemental oxygen use in PACU:** The total time in minutes that a patient received supplemental oxygen from arrival in PACU until being marked for discharge
- 5) **Reintubation rate:** The incidence of patients who required reinsertion of an endotracheal tube after the patient was extubated in the OR. This includes patients who were reintubated in the PACU or subsequently after PACU discharge.
- 6) **Unplanned Upgrade of Care:** The incidence, defined as a binary variable, of patients who were transferred to an ICU after being admitted to a non-ICU setting.
- 7) **Obstructive Sleep Apnea (OSA):** The presence of obstructive sleep apnea based upon previous structured data in the electronic medical record (EMR) such as prescriptions for CPAP, medical history and the anesthesiologist's preoperative note.

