12.0 ELIGIBILITY CRITERIA

12.1 Inclusion Criteria

One or more of the following:

1	Undergoing surgery at RR OR, SM OR
2	Obstructive or restrictive lung disease in EMR
3	Obstructive sleep apnea
4	Preoperative O2 saturation <95% (average/median of 12 hours before surgery)
5	BMI > 40
6	Acute respiratory infection within 1 month prior to surgery
7	Previous history of airway pathology

Two or more of the following:

1	BMI>35
2	Multiple intubation attempts
3	Surgical duration >2 hours
4	Upper abdominal surgery, intrathoracic surgery, or airway/head&neck surgery
5	Most recent Hb (within 6 months only) <10

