17.0 STUDY DATA COLLECTION

All aspects of the patient's management are at the discretion of the attending physician.

The following data will be collected and recorded in the eCRF:

Overall

- Admission ID
- Procedure name
- Primary CPT code
- Date of service
- UCLA location
- Case start time
- Case end time
- Procedure start time
- Procedure end time
- Emergency case status
- Case department name
- Obstructive respiratory lung disease
- OSA
- Preop SpO2
- BMI > 40
- Acute respiratory infection
- Airway pathology
- BMI > 35
- Multiple intubation attempts
- Surgery duration > 2 hrs
- Abdominal thoracic HN surgery
- Hgb less than 10 in 6 months
- Intraoperative sugammadex total?
- Sugammadex administered time
- Flag pushed in from PDW
- BPA fired in Epic
- Received rocuronium intraop
- Received study drug
- Enrolled patient
- PACU signout time
- Duration O2 saturation less than 90%
- Duration O2 saturation less than 95%
- Pathway compliance
- Postop reintubation
- Unplanned upgrade of care
- EARS study drug
- Inpatient death
- Bradycardia
- Anaphylaxis
- Reintubation

Baseline data

- Age

- Weight
- BMI
- ASA Physical Status Score
- Number of STOP Bang Criteria
- Existence of OSA on Problem List
- Previous Charting for OSA
- Previous Prescription for CPAP/BiPAP
- Lung Disease in problem list
- Abnormal PFT results
- Previous coding of lung disease
- Surgical procedure
- Oxygen saturation in preoperative area
- Preoperative Hemoglobin

Intraoperative Data

- Surgical duration
- Median PEEP
- Median TV
- Median FiO₂
- Maximum PEEP
- Maximum TV
- Maximum FiO₂
- Minimum PEEP
- Minimum TV
- Minimum FiO₂
- Time and dosage of administration of rocuronium
- Time, dosage and name of reversal agent
- All documented assessments of muscle strength (i.e. TOF ratio)
- Anesthesia Provider
- Time since most recent dosage of neuromuscular blocking agent
- Most recent train-of-four ratio prior to reversal.

PACU Data

- Time until ready to discharge
- Duration of supplemental oxygen therapy
- Minimum oxygen saturation
- Duration of oxygen saturation <95
- Duration of oxygen saturation <90
- Adverse events and protocol deviations, if applicable

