At this point, we estimate that the pathway will recommend sugammadex for all patients in the medium or high-risk groups as well as some patients in the low risk group (i.e. those patients requiring deep neuromuscular blockade to facilitate surgical conditions such as robotic procedures, free flap cases and others). Given the large number of patients, Merck would supply one vial of study drug for each patient. Thus the total amount of study drug would be no more than 6,500 patients for the one year intervention time.

Given 1 year of data, we observed an overall average PACU discharge time of 152.54 minutes (SD=623.86). With one year of post-data, we are adequately powered (90%) to pick up a reduction in PACU discharge time as small as 27.04 (two-sample t-test, alpha=0.025). Since the current difference in PACU discharge time between low and high risk groups is 67.52 (subtracting 216.62-149.10, see table), we feel the 27.04 minimally detectable difference gives us a great chance of detecting a meaningful difference.

Given 1 year of data (pre-period), we observed the rate of patients with any time SpO2<90% was 4.6% (574/12,467). With one year of post-data, we are adequately powered (90%) to pick up a reduction in this rate if it decreases to around 3.7% in the post (chi-square test, alpha=0.025). Since the current difference in patients with any time with SpO2<90% between low and high risk patients is 5.2% (subtracting 9.2%-4.0%), we feel the minimally detectable difference of 3.7% (4.6%-3.8%) is feasible.

Table 2.

	suppl O2, mean (SD)	PACU disch. Time, mean (SD)	Reintubation, freq (%)	Unplanned upgrade, freq (%)	SpO2<90%, freq (%)	SpO2<95%, freq (%)
OVERALL(n=13,277)	74.81 (241.82)	152.54 (623.86)	89 (0.7%)	138 (1.0%)	574 (4.6%)	6510 (52.3%)
low (n=9,841)	74.48 (280.55)	149.10 (599.78)	63 (0.6%)	111 (1.1%)	372 (4.0%)	4603 (50.0%)
medium(n=2,997)	74.98 (95.67)	154.43 (536.58)	23 (0.8%)	22 (0.7%)	164 (5.8%)	1658 (58.8%)
high (n=439)	79.54 (88.44)	216.62 (1321.46)	3 (0.7%)	5 (1.1%)	38 (9.2%)	249 (60.9%)
Smallest detectable difference (90% power)	9.61	24.84	0.4%	0.4%	3.8%	50.3%

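### The OSA entry label may draw on the index preoperative note, whose writers are trained and alerted only in the intervention year, so a shift in labelling could pass for a pathway effect on SpO2<90%

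*Combined protocol and SAP*

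**What the plan says.** Section 12.1 lists "Obstructive sleep apnea" among the conditions of which one is enough for entry. Section 26.0 and the SAP also use OSA to form the low, medium and high risk groups.

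Section 10.0, item 7, repeated in the SAP, defines it as "The presence of obstructive sleep apnea based upon previous structured data in the electronic medical record (EMR"), and names the sources: "such as prescriptions for CPAP, medical history and the anesthesiologist's preoperative note".

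Four features of the design bear on that definition:

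- **Comparator.** Section 25.2 takes the year before implementation as baseline. There is no concurrent control.
- **Training.** Section 8.0: "Clinicians will be trained prior to study go-live to ensure awareness and understanding of pathway procedures".
- **Alert.** Section 6.0 times the pop-up: "When the anesthesiologist completes the preoperative evaluation for a patient who is flagged as having either respiratory disease or OSA". Section 8.0 adds that the alert gives the reason for the high-risk designation.
- **Drug supply.** Section 26.0: "Merck would supply one vial of study drug for each patient".

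Section 17.0 collects OSA evidence by source: problem list, earlier charting, and "Previous Prescription for CPAP/BiPAP". Lung-disease coding and PFT results are also separate fields. No section ties the OSA definition to a date cut-off, and none plans a check on how often OSA is recorded over time.

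**The concern.** In a before/after comparison the label that selects patients must mean the same thing in both years. Here one listed source is written by the clinicians whose behaviour the pathway sets out to change. If, after go-live, they record suspected or mild OSA more readily, the labelled group takes in patients who would have stood in the low-risk group a year earlier. Its outcomes improve although no patient fares better.

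The planned methods give no firm protection. Matching on the label treats a newly labelled patient as equivalent to a baseline patient with established OSA. Other covariates might separate the two, but they are not fixed: Section 25.1 refers to a section 2.4, while Section 2.0 of this protocol is the abbreviation table, and the SAP says only that various variables may be used. Segmented regression would read a step in labelling at go-live as the level change due to the intervention.

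**Working it through.** **1. The plan's own figures.** With n = 13,277 per period and SD 623.86 (Table 2), the detectable difference is (z for alpha + z for power) × SD × √(2/n).

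- Alpha 0.05: (1.960 + 1.282) × 623.86 × √(2/13,277) = 24.82 min (SAP: 24.84).
- Alpha 0.025: (2.241 + 1.282) × 623.86 × √(2/13,277) = 26.97 min (Section 26.0: 27.04).
- SpO2<90%, 4.6% at baseline, 12,467 per period: detectable post-period rate 3.78% at alpha 0.05 (stated 3.8%) and 3.71% at alpha 0.025 (stated 3.7%).

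All reproduce.

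**2. Baseline rate in the labelled group.** Denominators back-calculated from Table 2:

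- low: 372/0.040 = 9,300
- medium: 164/0.058 = 2,828
- high: 38/0.092 = 413

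Medium plus high: (164 + 38)/3,241 = 6.23%. Low: 4.0%.

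**3. Relabelling with no treatment effect.** Let a share f of the low-risk group enter the labelled group in the post period only, with event rate r. Both f and r are assumptions.

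Post rate = (202 + r × 9,300f) / (3,241 + 9,300f)

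| f | Added patients | Growth of labelled group | Post rate, r = 4.0% | Fall, r = 4.0% (points) | Fall, r = 5.0% (points) |
|---|---|---|---|---|---|
| 5% | 465 | 14% | 5.95% | 0.28 | 0.15 |
| 10% | 930 | 29% | 5.74% | 0.50 | 0.28 |
| 20% | 1,860 | 57% | 5.42% | 0.81 | 0.45 |

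**4. Chance of a false favourable result.** This is a two-proportion test at two-sided alpha 0.025 (Section 25.1), so 1.25% in the favourable direction if there is no shift. For f = 10%, r = 4.0%: n = 3,241 and 4,171, pooled SE 0.00554, unpooled SE 0.00557, and Φ[(0.00498 − 2.241 × 0.00554)/0.00557] = 9%.

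- r = 4.0%: about 4%, 9% and 25% for f = 5%, 10% and 20%. Taking the low-risk denominator by subtraction (12,467 − 3,241 = 9,226, rate 4.03%) gives 24% for the last.
- r = 5.0%: about 2.4%, 4.0% and 8.3%.

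This is a crude comparison of the labelled groups. It does not simulate the matched analysis.

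**5. PACU time.** Medium plus high mean = (2,997 × 154.43 + 439 × 216.62)/3,436 = 162.4 min. Adding a share f of the 9,841 low-risk patients at 149.10 min lowers it by 1.7, 3.0 and 4.8 min for f = 5%, 10% and 20%. Relabelling every low-risk patient lowers it by 9.8 min.

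**The case against.** The strongest reply is that the definition already looks back. It speaks of previous data, and most of the OSA fields in Section 17.0 are worded that way. That is the more natural reading, but it is not secure: the note is listed without a date limit. The low-risk definition in Section 26.0, no documentation before surgery, does not exclude a note written before that same surgery.

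Several stronger readings are tempting, and the documents do not support them.

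- *The patient's own pop-up creates the label.* Section 6.0 shows it when the evaluation is completed, for a patient already flagged. Any drift would have to come from training and from alerts on earlier patients.
- *Labelling will widen.* No passage shows or predicts this. Training is on pathway procedures, sugammadex already made up 57.3% of reversals (Section 4.0), and the note is a listed source in the baseline year too.
- *Both primary outcomes are seriously biased.* For PACU time, the endpoint marked primary, even total relabelling gives less than half the stated detectable difference.
- *A 0.81-point fall matches the planned detectable effect.* That planned figure of about 0.8 to 0.9 points belongs to 12,467 patients per period at 4.6%. At 3,241 per period and 6.23%, the 90%-power detectable fall is about 1.8 points (alpha 0.05) or 1.95 (alpha 0.025). The error rates in the working are the fairer measure.
- *Matching makes matters worse.* The model is not specified. BMI, STOP-Bang count and preoperative saturation are collected and could separate mild from established OSA if they were used.

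Two further points stand. Newly suspected OSA patients are unlikely to carry the average low-risk rate, so 4.0% favours the concern. Many would also qualify by another route. Read literally, "Undergoing surgery at RR OR, SM OR" in Section 12.1 is sufficient alone, whereas the protocol summary makes surgery elsewhere an exclusion. Those two passages need reconciling, but Section 14.0 enrols patients considered high risk, so OSA is evidently meant to count.

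**Conclusion.** The point holds as a limited one. An entry and risk-group label may rest on a source exposed to the intervention in one period only, and the plan neither clearly excludes that source nor monitors it.

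The exposure is mainly on SpO2<90%, one of the two primary objectives. Under the assumptions shown, the spurious fall runs from about 0.15 to 0.81 points, and the false favourable rate from about 2.4% to 24 or 25%, against 1.25%. The upper end needs the labelled group to grow by 57% with patients at the average low-risk rate. The calculation also uses the simplified classes of Table 2 in place of the real criteria, and the other entry routes would shrink the effect further. For PACU time the artefact is minor.

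This does not show that the result will be biased. It is a cheap improvement worth making before the cohort is extracted.

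**What to change.** In Section 10.0 and the SAP, state that for the analysis cohort and the propensity score, in both years, OSA and lung disease are defined only from record data dated before the index preoperative evaluation: problem list, earlier charting or coding, earlier CPAP/BiPAP prescription and earlier PFT results. All are already collected under Section 17.0. The alert and its triggers stay as they are.

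Add two checks:

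- Report, month by month across go-live, the proportion of rocuronium or vecuronium cases labelled OSA, by source.
- Repeat the main analysis with the index note counted, as a sensitivity analysis.

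The cost is a date restriction in the data warehouse algorithm, a sentence in each document, one plot and one extra model run. The downside is that patients whose OSA is first recorded at the index evaluation leave the main analysis unless they qualify by another criterion. The sensitivity analysis shows whether that matters.

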11.0 STUDY POPULATION

UCLA RRUMC and UCLA Santa Monica patients aged 18 and older who had a general anesthetic with either rocuronium or vecuronium will be considered for inclusion in the study.

12.0 ELIGIBILITY CRITERIA

12.1 Inclusion Criteria

One or more of the following:

1	Undergoing surgery at RR OR, SM OR
2	Obstructive or restrictive lung disease in EMR
3	Obstructive sleep apnea
4	Preoperative O2 saturation <95% (average/median of 12 hours before surgery)
5	BMI > 40
6	Acute respiratory infection within 1 month prior to surgery
7	Previous history of airway pathology

Two or more of the following:

1	BMI>35
2	Multiple intubation attempts
3	Surgical duration >2 hours
4	Upper abdominal surgery, intrathoracic surgery, or airway/head&neck surgery
5	Most recent Hb (within 6 months only) <10

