	
 • Previous history of airway pathology 
Two or more:
 
 • BMI>35 • Multiple intubation attempts • Surgical duration >2 hours • Upper abdominal surgery, intrathoracic surgery, or airway/head and neck surgery • Most recent Hb (within 6 months only) <10
Exclusion Criteria	
 • Pregnant or lactating (or gave birth within last year) • Age<18 • Documentation of allergy or previous reaction to sugammadex • GFR<30 • Neuromuscular disease (ICD codes) • Remain intubated/tach post-op • Surgery at a site other than RR OR or SM OR
Study Endpoints	
 1) PACU Discharge Time (primary endpoint) 2) Incidence of oxygen saturation <90 3) Incidence of oxygen saturation <95% 4) Duration of supplemental oxygen use in PACU 5) Reintubation rate 6) Unplanned Upgrade of Care
Safety Evaluation	All adverse events reported by participating clinicians between enrollment and 48 hours after drug administration will be tabulated.
Study Procedures	
 • Retrospective analysis: PDW data extracted and analyzed to determine incidence of respiratory depression, changes in slope at time of sugammadex introduction, and associations between reversal practices and time to discharge from the PACU. Propensity score for postoperative respiratory dysfunction created. • Pathway creation and prospective pathway implementation: Core group creates pathway guidelines and associated decision support. Build CDS pathway into EMR and collect data following go-live date. 
CDS Pathway:
 
Preoperative Phase

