6.0 STUDY DESIGN

In order to allow for a learning curve associated with the introduction of sugammadex we will not include any patients for one year after sugammadex introduction.

Creation and implementation of a pathway to prevent postoperative respiratory dysfunction:

In order to improve outcomes for high-risk patients who receive general anesthesia and paralysis we will design and implement a perioperative decision support system which will identify high-risk patients and provide best practice recommendations via electronic clinical decision support reminders. While the exact parameters of the pathway will be designed based upon feedback from a group of quality leaders in the department (see Study Procedures below), in general the pathway will function as follows.

Patients will be identified based upon the aforementioned selection criteria. Patients meeting one or more of the following: Undergoing surgery at RRUMC OR, Santa Monica OR, obstructive or restrictive lung disease in EMR, obstructive sleep apnea, preoperative O2 saturation <95% (average/median of 12 hours before surgery), BMI>40, acute respiratory infection within 1 month prior to surgery, previous history of airway pathology; or two or more of the following: BMI>35, multiple intubation attempts, surgical duration >2 hours, upper abdominal surgery, intrathoracic surgery or airway/head and neck surgery, or most recent Hb (within 6 months) <10. Patients will be excluded if they are less than age 18, have co-existing renal disease with a GFR<30, neuromuscular disease, are pregnant or breastfeeding at the time of surgery, have an allergy to sugammadex or rocuronium, or patients who are expected to remain intubated after surgery or expected to leave the operating room with a tracheostomy in-situ.

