9.0 STUDY HYPOTHESIS

- 1) Sugammadex is a direct reversal agent for rocuronium that has been shown to be superior to reversal with neostigmine. We hypothesize that the introduction of sugammadex into clinical practice at our institution results in a decrease in respiratory dysfunction in the PACU.
- 2) Creation and implementation of a pathway that applies best practices (including reversal with sugammadex) to patients who have obstructive sleep apnea (OSA), or preexisting respiratory disease will decrease the incidence of short-term respiratory complications

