14.0 SUBJECT RECRUITMENT

During the screening phase, patients aged 18 and older who will have a general anesthetic with either rocuronium or vecuronium and who are considered high risk for postoperative pulmonary complications will be flagged in CareConnect and enrolled in the study. Clinicians will receive an alert identifying the patient as a subject in the study and will remind the clinician to pick up the study drug sugammadex from the pharmacy.

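### Section 6.0 counts surgery at the study operating rooms as a qualifying criterion, so as written no risk factor is needed; 12.1 repeats the item, and the Summary and 14.0 contradict it

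*Combined protocol and SAP*

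**What the plan says.** Protocol section 12.1 lists "Undergoing surgery at RR OR, SM OR" as row 1 of its one-or-more list. Six patient-level items follow: lung disease, sleep apnea, low preoperative saturation, BMI above 40, recent respiratory infection and airway history. A two-or-more list of five items comes next. No connector is printed between the lists.

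Section 6.0 gives the rule in prose: "Patients meeting one or more of the following: Undergoing surgery at RRUMC OR, Santa Monica OR, obstructive or restrictive lung disease in EMR". Where the two lists meet it reads "previous history of airway pathology; or two or more of the following: BMI>35". It introduces the rule with "Patients will be identified based upon the aforementioned selection criteria". The criteria apply to the population in section 11.0: "UCLA RRUMC and UCLA Santa Monica patients aged 18 and older who had a general anesthetic with either rocuronium or vecuronium".

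The Protocol Summary (3.0) differs. Its one-or-more list starts with lung disease and has no site item. Site appears among its exclusions, as "Surgery at a site other than RR OR or SM OR". Section 12.2 does not carry that exclusion. The Summary also prints no connector. Section 14.0 says that patients "who are considered high risk for postoperative pulmonary complications will be flagged in CareConnect and enrolled in the study". Hypothesis 2 (9.0) concerns "patients who have obstructive sleep apnea (OSA), or preexisting respiratory disease". The SAP does not restate the lists, so it does not settle the matter.

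**The concern.** A place of surgery is not a risk factor. Put in a list where any one item is enough, it makes the rest of that list redundant for everyone operated on in that place. The study aims at patients at high risk of respiratory complications, yet the rule in 6.0, read as printed, admits patients with no such risk.

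The wording matters because section 29.2.1 says each study element is built by an algorithm from the data warehouse, and an algorithm needs one rule. Three uses depend on it: the flag that triggers the alert, the baseline-year cohort (25.2), and the accrual reports of patients who meet the inclusion criteria (29.4.4).

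**Working it through.** No figure in the plan has to be reproduced for this point. The check is a comparison of rules.

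**Notation.** S = surgery in the RR or SM operating rooms. A = at least one of the six other first-list items. B = at least two of the five second-list items. Exclusions apply throughout.

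1. **Section 6.0:** (S or A) or B. For anyone operated on in those rooms S is true, so the rule is met whatever A and B are.
2. **Section 12.1, connector not printed:**
   - read with *or*: (S or A) or B, as in 6.0;
   - read with *and*: (S or A) and B, which reduces to B when S is true.

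   A drops out in both cases. Under either connector the six other first-list items have no selecting effect among patients operated on in those rooms.
3. **Protocol Summary:** S is required through the exclusion of other sites, and A and B are then joined by an unprinted connector. With 6.0's *or* this is S and (A or B).
4. **Difference between 6.0 and the Summary read with *or*:** patients with S true, none of the six items in A, and at most one of the five in B.

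**Evidence on intent.**
- Section 6.0 points back to criteria already given, and the only ones set out before it are in the Summary.
- Section 6.0 describes a system that picks out high-risk patients, and then a pop-up for patients flagged for respiratory disease or OSA.
- The alert in 8.0 labels the patient high-risk and gives the reason.
- Section 14.0 makes high risk a condition of enrollment.
- Section 17.0 has a field corresponding to each of the 6 + 5 = 11 non-site criteria (the lung-disease field names obstructive disease only) and records hospital location separately.

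All five point to a misplaced site row.

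**Scale.** The group in step 4 is not tabulated. The nearest figures are the simplified risk classes in 26.0:
- Table 1: 9,730 + 2,952 + 445 = 13,127; low class 9,730 / 13,127 = 74.1%.
- Table 2: 9,841 + 2,997 + 439 = 13,277; low class 9,841 / 13,277 = 74.1%.

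The low class means only that neither OSA nor respiratory disease was documented. Some of these patients would qualify on BMI, saturation, infection, airway history or the second list, so 74% is not the share wrongly admitted.

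**Where it would act.** In the intervention year, enrollment also requires that study drug be provided (13.0), and 29.4.3 treats its administration as an inclusion criterion. The baseline year has no such step. The 29.4.4 reports count patients with and without drug, so their denominator also rests on the written criteria.

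**The case against.** The strongest reply is that this is an obvious slip. Section 6.0 describes a risk-based flag both before and after the faulty sentence, and 8.0, 14.0, 17.0 and the Summary agree with that. This stands as evidence of intent, and it makes coding the flag for all comers unlikely. It does not remove the contradiction: the site item appears in two sections, one of them the formal eligibility section, and no section says that it is not a criterion. The sample sizes do not settle it either. Section 26.0 expects a prospective sample close to the roughly 13,000 yearly volume, while 7.0 gives 6,500.

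Stronger readings are tempting, but the documents do not support them:

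- *Section 12.1 does not select on risk at all.* That holds only if 6.0's *or* is carried over. Read with *and*, 12.1 still selects through the second list.
- *The site row shuts out patients with sleep apnea or lung disease.* Under *and*, those with fewer than two second-list items are left out whether or not the row is there. That comes from the missing connector, and 6.0 prints *or*.
- *As many as 9,730 patients would be wrongly admitted, and no more.* Table 2 gives 9,841 for the same class, neither table is stated to be limited to those operating rooms, and 7.0 and 26.0 expect some low-risk patients in the pathway.
- *The two periods were coded from different rules, so their case mix differs.* Nothing in the documents suggests this. Sections 29.2.1 and 29.4.3 describe one warehouse and standardized procedures.

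**Conclusion.** The contradiction is real and should be fixed. As written, 6.0 admits every non-excluded patient in the 11.0 population operated on in the two sets of operating rooms, with no risk factor required. Section 12.1 does the same if read with 6.0's connector. The Summary, 14.0 and the rest of 6.0 describe a different, risk-selected cohort. The evidence favors a misplaced site row, though that is an inference.

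The effect cannot be sized from the documents. The low class, about 74% in both tables, shows only how much of the yearly volume lacks documented OSA or respiratory disease. The study-drug requirement limits the effect in the intervention year. The baseline cohort and the accrual denominator have no such limit. A reader might infer that the cohort has been built wrongly, but the documents show only that the written rule would permit it.

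**What to change.** - Take the site item out of the one-or-more list in 6.0 and 12.1. State surgery in the RR or SM operating rooms as a separate mandatory condition, or carry the Summary's off-site exclusion into 12.2.
- Have the authors reconcile 6.0, 12.1 and the Summary, and print one connector between the two lists in all three. Only 6.0 prints one now, and it is *or*.
- Confirm that the EMR flag, the baseline-year cohort and the 29.4.4 accrual reports all use that single rule.

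The cost is a wording amendment and a check of the extraction logic. No new data are needed.

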25.2 Prospective analysis

The prospective analysis will largely follow a similar framework however we will focus on the primary and secondary outcomes as described above and will use a one year period prior to implementation as our baseline.

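### Two criteria in 12.1 cannot be known when patients are flagged, and no rule says how 12.1 applies to the baseline year, so the two periods may be selected on different information

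*Combined protocol and SAP*

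**What the plan says.** Section 12.1 admits a patient who has one item from a first list or two from a second list of five. The second list contains "Surgical duration >2 hours" and "Multiple intubation attempts". Neither is qualified as scheduled, expected or historical. Other items are anchored in time: preoperative saturation to the 12 hours before surgery, respiratory infection to the preceding month, hemoglobin to the last six months, and airway pathology to previous history.

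The eligibility decision is used before the operation:

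- Section 14.0: during screening, patients "who are considered high risk for postoperative pulmonary complications will be flagged in CareConnect and enrolled in the study".
- Section 6.0 places the reminder at this moment: "When the anesthesiologist completes the preoperative evaluation for a patient who is flagged".
- Section 8.0, preoperative phase: "Physicians/CRNAs will receive an alert identifying the patient as high-risk for postoperative pulmonary complications and the reason for the designation". The same notification prompts collection of study drug.

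Section 17.0 lists surgical duration under intraoperative data and also collects "Procedure end time". For the comparison group, Section 25.2 says only that the analysis "will use a one year period prior to implementation as our baseline". The SAP (Statistical Methods) adds nothing to this.

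**The concern.** The eligibility rule cannot be carried out in full at the moment it is used. A site or programmer must substitute something for the two items, and the protocol does not say what.

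Suppose an upper abdominal case, with no other item, is booked for 90 minutes and runs to 150. It meets 12.1 on the finished record but could not have been flagged on duration. If a similar case is booked for 150 minutes and ends at 100, a flag based on booking would catch it, although it fails 12.1 as written.

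The baseline year had no pathway (Section 26.0) and so no live flag. Its eligible patients must be reconstructed from warehouse records, where realised duration and attempts are available. A before/after comparison depends on one selection rule in both periods. Without one, part of any difference in PACU time or hypoxemia may reflect who was counted rather than what the pathway did.

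**Working it through.** **The plan's own figures, for scale.** Smallest detectable difference = (z for two-sided alpha + z for power) × SD × √(2/n). With SD 623.86, n = 13,277 per period (Table 2, equal periods assumed), alpha 0.025 and power 90%, this is (2.241 + 1.282) × 623.86 × √(2/13,277) = 26.97 minutes; Section 26.0 states 27.04. For SpO2<90%, a fall from 4.6% to 3.7% with 12,467 per period at alpha 0.025 has power 0.909; the protocol states 90%. This point disputes neither figure.

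**Who is affected.** Only patients with no item from the first list who need duration or attempts to reach two from the second. The documents do not give their number. A loose ceiling comes from Table 2: medium plus high patients number 2,997 + 439 = 3,436. If 6,500 are eligible, 1 - 3,436/6,500 = 47% qualify by some route other than OSA or lung disease. The affected group is some part of these.

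**Can the sign be determined?** Assume no pathway effect and a complete mismatch: the baseline contains group A (eligible on preoperative information) and group B (eligible only through the two items), while the pathway cohort contains A alone. With B a share s of the baseline,

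apparent difference (pathway minus baseline) = s × (rate in A - rate in B).

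Stand-in for A, from Table 2's medium and high classes:

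- SpO2<90%: (164 + 38) / (164/0.058 + 38/0.092) = 202/3,240.6 = 6.233%.
- PACU time: (2,997 × 154.43 + 439 × 216.62)/3,436 = 162.38 minutes.

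B is set to Table 2's low value (4.0%; 149.10 minutes) and then its high value (9.2%; 216.62 minutes). The shares are assumptions.

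| Share s | SpO2<90%, B at 4.0% | SpO2<90%, B at 9.2% | PACU, B at 149.10 | PACU, B at 216.62 |
|---|---|---|---|---|
| 10% | +0.22 points | -0.30 | +1.33 min | -5.42 |
| 20% | +0.45 | -0.59 | +2.66 | -10.85 |
| 47% | +1.05 | -1.39 | +6.24 | -25.49 |

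For example, 0.10 × (6.233 - 4.0) = +0.22 and 0.10 × (6.233 - 9.2) = -0.30. A plus sign makes the pathway look worse, a minus sign better, and the difference is zero when B's rate equals A's. The table is a sign test and does not estimate the bias. It ignores matching and cases wrongly flagged on scheduled duration. Group A would also include patients who qualify through BMI or other preoperative items, whose rates are not given.

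**The case against.** - **The baseline may not use realised values.** Correct: no text says it will. A scheduled duration could serve both periods, or both could be classified afterwards from the same Section 17.0 fields. Section 29.4.4 also shows that eligible patients without study drug can be identified. The mismatch is therefore a risk left open by the plan, while the absence of a rule is a fact.
- **The flag might be updated during the case.** Section 8.0 has an intraoperative reminder to get study drug, and intubation attempts are known well before reversal. But no text says that risk status is recalculated.
- **Propensity matching could help.** It could, if the right covariates were carried over. Section 25.1 refers to a section 2.4 for its variables, which this protocol does not contain, and Section 25.2 promises only a broadly similar framework.
- **Item 1 of 12.1 makes the question moot.** Read literally, surgery at either site qualifies everyone. However, Section 14.0 restricts enrolment to high-risk patients, and the synopsis instead excludes surgery elsewhere. These texts conflict and need reconciling.

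A reader might also infer that the mismatch flatters the pathway, since overruns and difficult airways sound like the worse cases. The documents do not support this. Patients who qualify only through the second list have neither OSA nor lung disease, because either would qualify them alone. In Section 26.0's classes they are low risk (4.0%), below the 6.2% of the medium and high classes combined. Long surgery or obesity may raise their risk, but by an amount the documents do not give.

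**Conclusion.** The concern holds as a defect in the selection rule. Two of the five second-list criteria are, as worded, unobservable at the preoperative flag, and nothing says how 12.1 is applied to the baseline year. If the periods end up selected on different information, the comparison is biased by an amount and in a direction that the documents do not allow one to state. Neither a claim that the pathway is favoured nor any single figure for the bias is justified.

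Unknown direction does not make it harmless: the plan aims to detect a change of about 0.9 points (4.6% to 3.7%). A second asymmetry belongs with it. Section 13.0 defines enrolment by provision of study drug, and Section 29.4.3 makes its administration a condition of inclusion. No baseline patient can meet that condition. The rule should be fixed before outcomes are examined, since a later choice would be post hoc.

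**What to change.** For the analysis cohort only:

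1. State the time point and data source for every criterion, using information available at the preoperative flag. For example, use scheduled duration over two hours, and count intubation attempts only if documented before the index case; otherwise leave that item out of cohort selection.
2. Run the same warehouse algorithm on baseline-year and post-go-live records, as of the preoperative time point.
3. Include every patient who meets it, whether or not study drug was provided or given.
4. Keep realised duration and realised attempts as descriptive data.
5. Reconcile item 1 of 12.1, repeated in Section 6.0, with the synopsis.

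The cost is a wording amendment and one algorithm run on both periods. Scheduled duration and prior intubation attempts are not in the Section 17.0 list and must be added to the extract. Patients whose high risk appears only during the case leave the comparison cohort; their care need not change. Including eligible patients without study drug means that the result describes the pathway as rolled out, not the drug as given.
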